3.13.2.1. Pregnancy Test

All subjects of childbearing potential must have a negative pregnancy test at Screening and Day 1 to be enrolled in the study. All subjects of childbearing potential will undergo a serum pregnancy test at Screening and urine pregnancy tests at Day 1, Day 22, Day 43, Day 71, Day 161, and Day 251. Results must be available prior to study treatment and prior to MRIs. A subject who becomes pregnant must immediately be discontinued from study treatment and be withdrawn from the study.

3.13.3. Vital Signs

Vital signs (systolic and diastolic blood pressure, respiratory rate, pulse rate, body temperature) will be collected at Screening, Day 1, Day 22, Day 43, Day 71, Day 161, and Day 251, after the subject has been seated for 5 minutes (minimum).

On study treatment days (Days 1, 22, and 43), vital signs will be taken up to 4 hours prior to dosing and at 15 minutes and 30 minutes after dosing (body temperature is not required at the 15-minute post dose time point). The subject's vital signs must be stable or repeated until stable before the subject can leave direct observation.

Any clinically significant abnormality in vital sign observed, will be considered as an AE or SAE as appropriate.

3.13.4. 12-Lead Electrocardiogram (ECG)

A 12-lead ECG will be performed at Screening while the subject is in the supine position for at least 5 minutes.

The ECG recording should include a minimum of 5 heart cycles (beats). If the ECG report shows QT prolongation with $QTc \geq 450$ ms, the investigator should repeat the ECG within 1 hour. If the initial findings are confirmed, the investigator should exclude the subject from study participation.

The ECG will be interpreted by the investigator and graded as:

- Normal.
- Abnormal, not clinically significant.
- Abnormal, clinically significant.

Any clinically significant abnormality in ECG observed, will be considered as an AE or SAE as appropriate.

3.13.5. Physical Examination

A complete physical examination (by body system) will be performed at Screening. A complete physical evaluation will include an examination of head, eyes, ears, nose, throat, neck (including thyroid), cardiovascular system (including assessment of heart, peripheral pulses, presence or absence of edema), lungs, abdomen (including liver and spleen, bowel sounds), lymph nodes, musculoskeletal system (including spine, joints, muscles) neurological system (including cranial nerves, reflexes, sensation, strength), skin (excluding cellulite), extremities, and any other conditions of note.

Physical examination findings will be recorded as normal or abnormal.

If physical examination findings meet the investigator's criteria for clinical significance, then it will be reported as an AE or SAE as appropriate.

3.13.6. Height and Weight

Height will be collected at Screening. Weight will be collected at Screening, Day 1, Day 22, Day 43, Day 71, Day 161, and Day 251. If change in subject weight from Screening to subsequent visits meets the investigator's criteria for clinical significance, then it will be reported as an AE or SAE as appropriate.

3.13.7. Fitzpatrick Skin Scale

The Fitzpatrick Skin Scale is used for assessment of skin color and propensity for tanning. Fitzpatrick skin type for all subjects will be determined at Screening.

The Fitzpatrick Skin Scale is a 6-level scale (Types I-VI) ranging from 1 to 6 as mentioned in [Table 8](#) below.

Table 8: Fitzpatrick Skin Scale

Level	Description
1	Type I: Pale white skin, blue/hazel eyes, blond/red hair; Always burns, does not tan
2	Type II: Fair skin, blue eyes; Burns easily, tans poorly
3	Type III: Darker white skin; Tans after initial burn
4	Type IV: Light brown skin; Burns minimally, tans Easily
5	Type V: Brown Skin; Rarely burns, tans darkly easily
6	Type VI: Dark brown or black skin; Never burns, always tans darkly

3.13.8. Immunogenicity Samples

Immunogenicity variables include anti-AUX-I /anti-AUX-II (anti-drug antibodies) and neutralizing antibody results. Serum samples will be collected at Day 1 (prior to study treatment administration), Day 71, Day 161, and Day 251 for all subjects for the determination of serum anti-AUX-I and anti-AUX-II antibody levels and neutralizing antibodies to AUX-I and AUX-II.

3.13.9. Follow-up Biopsy

The investigator will examine the biopsy site for evidence of ongoing AEs related to the biopsy and will determine if the biopsy site has healed. The follow-up biopsy examination will be conducted at the Day 1, Day 85 and Day 265 visits. The investigator will examine and confirm sufficient healing of the biopsy site before dosing on Day 1.

3.14. Pharmacodynamics

Prior to the first MRI and biopsy, the investigator will select 3 dimples from the 2 treatment areas (both buttocks or both thighs) for MRI and biopsy evaluation from the 4 well-defined, isolated dimples that are considered moderate or deep in depth identified at Screening. The 3 selected dimples should be distributed across both regions of the treatment area (eg, 1 dimple on the left thigh [or buttock] and 2 dimples on the right thigh [or buttock], or vice versa). The investigator or designee will mark and label these 3 dimples for MRI and biopsies. The MRI technician or designee will locate the marked dimples and place an MRI coil appropriately on the dimple and photograph each dimple with the coil in place in a manner that will allow them to be relocated for subsequent MRIs.

3.14.1. MRI

MRI will be performed at Screening, Day 71 and Day 251. The Screening MRI will be performed after all other screening assessments, except the biopsy, are completed. Screening, Day 71, and Day 251 MRIs may be repeated as often as necessary to obtain an evaluable image. Repeat screening MRIs must take place within the screening window. The Day 71 and Day 251 MRI may be performed up to 7 days prior to the Day 71 and Day 251 visits respectively. The MRI must be completed before the biopsy at each visit. The Screening MRI will be done on all 3 selected dimples whereas the Day 71 and Day 251 MRI will be done on Dimple 2 & 3 and Dimple 3 respectively.

The Day 251/Early Termination MRI is not required for subjects who withdraw from the study (early termination).

3.14.2. Double Punch Biopsy

Biopsies will be performed at Screening, Day 71 and Day 251. The Screening biopsy will be performed on Dimple 1 after all other screening assessments, including MRI, are completed. The Screening biopsy will be performed at least 14 days prior to the Day 1 Visit.

The Day 71 biopsy will be performed on Dimple 2 and the Day 251 biopsy will be performed on Dimple 3 after completion of imaging for efficacy, PR-PCSS, and CR-PCSS at Day 71 and Day 251 respectively.

The Day 251/Early Termination biopsy is not required for subjects who withdraw from the study (early termination).

4. STUDY PARAMETERS

4.1. Subject Disposition

4.1.1. Discontinuation of Study Treatment

Subjects will be considered as completing the treatment phase if they complete Day 71 visit. Subjects discontinued from study treatment are those who discontinued the study at any time before completing all treatment phase visits. The date of, and reason for, study treatment discontinuation will be recorded in the eCRF.

If a subject becomes pregnant during the active treatment phase of the study (Day 1 through Day 43) then the study treatment will be permanently discontinued for that subject. Study treatment will also be discontinued if abnormal liver function is observed.

Subjects who discontinue from study treatment at any time after the first dose of study drug will not be replaced.

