^a Performed prior to any study-required assessments, unless exceptions granted for standard of care procedures. A separate informed consent may be used for HIV testing and must be signed before the sample is collected, if required.

^b Should be reassessed and verified prior to dosing.

^c Vital signs will be collected up to 4 hours prior to, and at 15 and 30 minutes after, study treatment administration on Days 1, 22, and 43.

^d Urine pregnancy test should be completed prior to the MRI.

^e At screening all 4 potential treatment areas (each buttock and each thigh) will be imaged; and CR-PCSS, PR-PCSS, and Hexsel CSS assessments will be done for each potential treatment area (each buttock and each thigh).

^f Before and after marking dimples for treatment. No manipulation of the treatment area should be done prior to the “before” photographs.

^g Screening MRIs will be performed after all other screening assessments (except the biopsy) have been completed. MRIs may be repeated within the screening window as often as necessary to obtain evaluable images.

^h The Day 71 and Day 251 MRIs may be performed up to 7 days prior to the indicated visit. The MRI must be completed before the biopsy required for these visits. The Day 251/Early Termination MRI is not required for subjects who withdraw from the study (early termination). The Day 71 and Day 251 MRIs may be repeated as often as necessary to obtain an evaluable image.

Table 1: Schedule of Activities (Continued)

ⁱ The screening biopsy will be performed after all other screening assessments (including MRI) are completed. The screening biopsy will be performed at least 14 days prior to the Day 1 Treatment Visit. The investigator must examine and confirm sufficient healing of the biopsy site before dosing on Day 1. The timing of all subsequent visits will be based on the actual date that the first dose of CCH is administered.

^j The Day 71 and Day 251 imaging for efficacy, PR-PCSS, and CR-PCSS must be completed prior to the biopsy sample collection required at those visits. The Day 251/Early Termination biopsy is not required for subjects who withdraw from the study (early termination). For subjects who received less than 3 doses of CCH prior to 18 March 2020, no Day 71 or Day 251 biopsy samples will be collected.

^k Visit not required for subjects who had less than 3 doses of CCH prior to 18 March 2020.

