4. STUDY DESIGN

4.1. Overall Design

This is a single-center, open-label, Phase 2a study to assess the safety and efficacy of CCH in adult women with moderate or severe EFP of the buttocks or thighs using photonumeric scales, MRI, and histopathology of tissues from the treated area. Approximately 19 subjects will be dosed in this study.

This study was suspended due to the COVID-19 public health emergency on 18 March 2020. When the study re-opens, subjects who had received less than 3 doses of CCH prior to 18 March 2020 will be allowed to continue in the study and may receive any remaining doses with Sponsor approval. These subjects will complete all remaining visits and assessments EXCEPT biopsies and biopsy follow-up visits, if willing to do so. These subjects will be included in the safety assessments for the study, but will not be included in the efficacy assessments. Subjects who received less than 3 doses prior to 18 March 2020 may elect to remain in the study without receiving additional doses.

Subjects who received all 3 doses of CCH prior to 18 March 2020, will be allowed to continue in the study and complete all remaining visits and assessments (including biopsies and biopsy follow-up visits), if willing to do so. These subjects will be included in the safety assessments for the study, but will not be included in the efficacy assessments. Subjects who received all 3 doses of CCH prior to 18 March 2020 may elect to remain in the study without completing the biopsies and biopsy follow-up visits.

An additional 12 subjects will be dosed in the study. These subjects will be included in the safety assessments, and all efficacy assessments will be based on the data from these 12 subjects. For the 12 subjects who receive their first dose of study drug after 18 March 2020, every attempt will be made to enroll an equal number of subjects across the 2 severity levels in both buttocks and thighs (eg, 3 subjects with moderate buttock cellulite, 3 subjects with severe buttock cellulite, 3 subjects with moderate thigh cellulite, and 3 subjects with severe thigh cellulite).

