4.4. End of Study Definition

A subject will be considered to have completed the study if the subject received their first dose of study drug after 18 March 2020 and completed the Day 265 visit. Subjects who received their first dose of study drug prior to 18 March 2020 and complete the Day 265 Visit (or the Day 251 Visit if they elect not to have biopsies) also will be considered to have completed the study.

The end of the study is defined as the completion of the final assessment for the last subject enrolled in the trial.

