7. DISCONTINUATION FROM STUDY TREATMENT AND SUBJECT DISCONTINUATION/WITHDRAWAL

7.1. Discontinuation of Study Treatment

Subjects who receive at least 1 dose of study treatment and discontinue study treatment or who are withdrawn from the study will be encouraged to complete the remaining study visits and evaluations and provide any additional follow-up information as required by the study, unless the subject specifically indicates that they will not participate in any further evaluations. The date of, and reason for, study treatment discontinuation will be recorded.

Permanent study treatment discontinuation is required for the following:

- The subject becomes pregnant during the active treatment phase of the study (Day 1 through Day 43).

Discontinuation of study treatment for abnormal liver function should be considered by the investigator when a subject meets one of the conditions outlined in Section [10.6](#).

If a clinically significant cardiac finding is identified (including but not limited to changes from baseline in corrected QT [QTc] interval) after the start of study treatment, the investigator or a qualified designee will determine if the subject can continue in the study and if any change in management is needed.

All subjects dosed prior to 18 March 2020 will be replaced. Subjects who receive their first dose of study drug after 18 March 2020 and subsequently discontinue from study treatment will not be replaced.

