4.1.2. Subject Withdrawal from the Study

Subjects will be considered as completing the study if they complete the Day 265 visit. Withdrawn subjects are those who withdrew the study at any time before study end. The withdrawal date and reason will be recorded in the eCRF.

Subjects who withdrew from the study should undergo all early termination assessments. A subject who becomes pregnant at any time during the study will be permanently withdrawn. Subjects who have been withdrawn from the study will not be replaced.

The reason for early discontinuation will be recorded in the eCRF for the subjects who do not complete the study. The reason for screen failure will also be recorded in the eCRF for subjects who are not enrolled and are considered screen failures.

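### SAP disposition rules follow visits, not doses: women who stop dosing can count as completing the treatment phase, and interrupted women who attend every required visit can count as study non-completers

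*SAP*

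**What the plan says.** **Treatment.** SAP 4.1.1 sets the completion rule: "Subjects will be considered as completing the treatment phase if they complete Day 71 visit". The next sentence sets the opposite category: "Subjects discontinued from study treatment are those who discontinued the study at any time before completing all treatment phase visits". Neither mentions the number of sessions received. SAP 7.1 uses these categories in the disposition table, by treatment region and overall, with reasons for leaving the study and reasons for stopping study drug as separate items.

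The protocol keeps stopping drug apart from leaving the study. Section 7.1 says that dosed subjects who "discontinue study treatment or who are withdrawn from the study will be encouraged to complete the remaining study visits and evaluations". Section 4.1 adds, for those caught by the suspension: "Subjects who received less than 3 doses prior to 18 March 2020 may elect to remain in the study without receiving additional doses".

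**Study.** SAP 4.1.2 reads: "Subjects will be considered as completing the study if they complete the Day 265 visit". It has no exception. The protocol has two:

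- Footnote k of the Schedule of Activities (protocol 1.2), attached to the Day 85 and Day 265 biopsy follow-up, says: "Visit not required for subjects who had less than 3 doses of CCH prior to 18 March 2020". Protocol 8.2.9 repeats the waiver.
- Protocol 4.4 accepts, for women first dosed before the suspension, the Day 265 visit "or the Day 251 Visit if they elect not to have biopsies".

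The Last Date in the Study entry in SAP Table 12 offers Day 265 for completers and otherwise only early termination or loss to follow-up.

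**The concern.** A disposition table should show how many women had the full course, how many stopped the drug and why, and how many finished the study. Under SAP 4.1.1 a woman who stops after one or two sessions and still attends Day 71 is in the first group and not the second. This could happen to any of the 12 new women, because protocol 7.1 applies to everyone dosed. It is most likely among the interrupted women, who may stay without further doses.

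The disposition table could then disagree with two other tables in the same report: adverse events leading to drug interruption or discontinuation (SAP 7.7.2), and subjects treated at each session (SAP 7.7.1).

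The study-completion rule errs the other way. A woman whose last required visit is Day 251 can do all that is asked of her and still lack the completer flag, and Table 12 has no entry that describes her last date. With 19 women dosed, each misclassification moves a percentage by about 5 points (1/19 = 5.3%).

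**Working it through.** No power or sample-size formula applies; this is a count.

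**Inputs**

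- Interrupted women dosed before 18 March 2020: 7, of whom 2 had 3 doses and 1 had 2 doses (protocol 2.1).
- New women: 12; total to be dosed: about 19 (protocol 4.1).
- Day 265 not required for women with fewer than 3 doses before the suspension (protocol 1.2 footnote k, 8.2.9).
- Women with 3 doses before the suspension may decline biopsies and the biopsy follow-up visits (protocol 4.1).

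**Check of the plan's total.** 7 + 12 = 19, which matches the protocol.

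**Dose split.** 7 − 2 − 1 = 4 women with 1 dose; 4 + 1 = 5 with fewer than 3.

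**Treatment.** Assume all 19 attend Day 71 and all 12 new women receive 3 sessions. Let k be the number of the 5 who never reach 3 doses. The SAP rule gives 19/19 whatever k is. The number with all 3 sessions is 12 + 2 + (5 − k) = 19 − k.

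| k | SAP: completed treatment phase | Received all 3 sessions |
|---|---|---|
| 0 | 19/19 | 19/19 (100%) |
| 1 | 19/19 | 18/19 (94.7%) |
| 2 | 19/19 | 17/19 (89.5%) |
| 3 | 19/19 | 16/19 (84.2%) |
| 4 | 19/19 | 15/19 (78.9%) |
| 5 | 19/19 | 14/19 (73.7%) |

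The same k women do not meet the SAP definition of discontinued from study treatment, because they have not left the study.

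**Study.** Assume every woman attends exactly the visits required of her. Let b be the number of the 2 three-dose interrupted women who have biopsies and so attend Day 265. SAP completers = 12 + b; non-completers = 7 − b.

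| b | SAP completers | Non-completers with all required visits done |
|---|---|---|
| 0 | 12/19 (63.2%) | 7/19 (36.8%) |
| 1 | 13/19 (68.4%) | 6/19 (31.6%) |
| 2 | 14/19 (73.7%) | 5/19 (26.3%) |

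If Day 251 counts for interrupted women who have no biopsies, which is the evident aim of protocol 4.4, the figure is 19/19. Taken word for word, protocol 4.4 helps only women who choose not to have biopsies. Protocol 8.6.2 says that the 5 women with fewer than 3 doses will not have them, so they make no such choice. The literal count is then 12 + 2 = 14/19.

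**The case against.** The best defence is that the rest of the SAP already shows what this table might hide.

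- **A reader might infer that tolerability is understated, or that no reason for stopping is tabulated.** The documents do not support that. SAP 7.7.2 counts adverse events leading to study drug interruption or discontinuation, overall and by preferred term, with a listing. SAP 7.7.1 gives the number treated, the injections and the dose at each session. SAP 4.1.1 has the date and reason for stopping treatment recorded, and SAP 7.1 plans a summary of reasons for stopping study drug. What remains is narrower: the definition in 4.1.1 decides who enters that summary, and it leaves out women who stop dosing but stay.
- **A reader might infer that withdrawals are overstated.** They are not. SAP 4.1.2 defines withdrawn subjects as those who leave before the end of study. A woman who finishes at Day 251 as planned has not withdrawn; she only lacks the completer flag.
- **The SAP speaks of completing the treatment phase, not of completing treatment.** That is fair, and the visit-based label is harmless alone. The difficulty arises because the matching definition of treatment discontinuation also ignores doses.
- **The study-completion mismatch is a consequence of timing.** SAP section 8 rests on the original protocol and Amendment 1, before the suspension. This explains the missing exception but does not supply one. It does not explain SAP 4.1.1, whose conflict with protocol 7.1 applies equally to the new women.
- **The loose wording in protocol 4.4 is minor.** Agreed: its intent is clear, and a short clarification would settle it.

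**Conclusion.** The point holds as a fault in the disposition rules and no further. Under SAP 4.1.1, women who stop dosing but attend Day 71 count as completing the treatment phase and fall outside the drug-discontinuation row. Under SAP 4.1.2, 5 to 7 of 19 women (26% to 37%) can attend every required visit and be non-completers.

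The treatment contrast is 19/19 against a range of 14 to 19 of 19 (74% to 100%). The lower end should not be quoted alone: it needs all 5 women with fewer than 3 doses to end short of the full course while attending Day 71, and protocol 4.1 lets them receive remaining doses with sponsor approval. Any new woman who stops early but attends Day 71 would add to the gap. The study range does not depend on whether the 5 resume dosing. It assumes that women excused from Day 265 do not attend it. A three-dose woman who has biopsies and attends Day 265 is correctly classified.

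Efficacy results are not affected. The protocol bases efficacy on the 12 new women, and the Evaluable Population in neither document uses a completion flag. The correction should be made, because otherwise the disposition table can contradict protocol 4.4 and the trial's own safety tables.

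**What to change.** **SAP 4.1.1.** Define treatment completion as all 3 sessions received. Define treatment discontinuation as permanent cessation of study drug, with its recorded reason, whatever visits follow. Add a separate flag for a missed session followed by later dosing; a rule that called everyone short of 3 sessions discontinued would mislabel a woman who missed one session and was dosed at the next. Report completion of the Day 71 visit as its own line, and use these definitions in the SAP 7.1 table.

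**SAP 4.1.2 and Table 12 (Last Date in the Study).** Adopt protocol 4.4: Day 265, or Day 251 for women first dosed before 18 March 2020 who have no biopsies.

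**Protocol 4.4.** Reword the Day 251 exception so that it covers women for whom biopsies are not performed as well as those who decline them.

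**Cost.** SAP wording, a few derivation flags, and a one-line protocol clarification. Dosing is already recorded at each visit (protocol 6.6), and the reason for stopping is already collected, so no new data are needed.

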4.1.2. Subject Withdrawal from the Study

Subjects will be considered as completing the study if they complete the Day 265 visit. Withdrawn subjects are those who withdrew the study at any time before study end. The withdrawal date and reason will be recorded in the eCRF.

Subjects who withdrew from the study should undergo all early termination assessments. A subject who becomes pregnant at any time during the study will be permanently withdrawn. Subjects who have been withdrawn from the study will not be replaced.

The reason for early discontinuation will be recorded in the eCRF for the subjects who do not complete the study. The reason for screen failure will also be recorded in the eCRF for subjects who are not enrolled and are considered screen failures.

